7.4. General Medical History

Medical history verbatim terms as recorded on the OLE eCRFs will be mapped to preferred terms (PTs) and system organ classes (SOCs) using MedDRA version 19.0.

Medical history collected during NEOD001-OLE001 will be summarized by SOC and PT using the OLE Safety Population. Summaries will be ordered by descending order of NEOD001-OLE001 24 mg/kg incidence of SOC and PT within each SOC.

General medical history will be presented in a by-subject data listing.

7.5. Pre-Treatment, Prior, and New Concomitant Medications

Medication verbatim terms as recorded on the OLE eCRFs will be mapped to Anatomical Therapeutic Chemical (ATC) class and Preferred Name using the WHO Drug Dictionary, B2 Enhanced December 2015.

Pretreatment medications, recorded on the Concomitant Medications eCRF, are those medications with start and stop dates prior to the first infusion of study drug in the OLE. Prior concomitant medications are those medications started prior and continued after the first infusion of study drug in the OLE. New concomitant medications are those medications that were started

on or after the first infusion of study drug in OLE. Concomitant chemotherapy is described in Section 7.7. If it cannot be determined whether the medication was a new concomitant medication due to a partial start or stop date or if the medication is taken on the same date as the first infusion of study drug, then it will be counted as a new concomitant medication.

Pretreatment medications will be listed only. Prior and new concomitant medications will be summarized by WHO ATC level 3, WHO ATC level 4, and preferred name using the OLE Safety Population. Prior and new concomitant medications will also be summarized separately as well. These summaries will present the number and percentage of subjects using each medication. Subjects may have more than one medication per ATC level and preferred name. At each level of subject summarization, a subject is counted once if he/she reported one or more medications at that level. Each summary will be ordered by descending order of NEOD001 incidence of ATC level and preferred name within each ATC level.

7.6. Premedication

Subjects may be premedicated with 25 mg diphenhydramine (or an equivalent dose of a H1 antihistamine) and 650 mg acetaminophen (or an equivalent paracetamol dose) within 30-90 minutes prior to study drug administration. Premedications will be mapped to ATC class and Preferred Name using the WHO Drug Dictionary, B2 Enhanced December 2015 and listed.

7.7. Chemotherapy

Chemotherapy regimens may be prescribed as per standard of care at the Investigator's discretion. All chemotherapy recorded on the Prescribed Chemotherapy Regimens and Concomitant Chemotherapy Treatment Medications eCRFs will be listed for OLE Safety Population.

7.8. Concurrent Procedures

Data will be collected for concurrent procedures will be mapped to PTs and SOCs using MedDRA version 19.0. and will include name of procedure, ongoing status, indication, relationship to an AE or medical history, and frequency of the procedure. Concurrent procedures will be displayed in a subject data listing only for OLE Safety Population.

8. EFFICACY ANALYSES

All recorded efficacy endpoint data will be presented in by-subject data listings for the OLE Safety Population. No summary tables or figures will be produced for the efficacy endpoints.

8.1. Adjustments for Covariates

Not applicable.

8.2. Handling of Dropouts or Missing Data

For the SF-36v2, missing data conventions for partially completed questionnaires are specified in Section [2.3.3.2](#).

No imputations will be performed on missing data.

8.3. Interim Analyses and Data Monitoring

Not applicable.

8.4. Multicenter Studies

This is a multicenter study and data collected from all study centers will be listed.

8.5. Multiple Comparisons/Multiplicity

No adjustments for multiplicity will be made.

9. SAFETY ANALYSES

Safety analyses will be conducted using the NEOD001 and OLE Safety Populations as specified below.

No inferential comparison of safety endpoints will be performed, unless otherwise specified.

9.1. Extent of Exposure

Study drug exposure during the OLE and separately for the original parent study (NEOD001-001) and OLE combined will be summarized including:

- Total Number of Infusions received will be determined for each subject by number of times the start time of drug infused is reported. If multiple infusion start times are reported on a single day, then only 1 infusion will be counted for that day. If the start time of drug infused is missing but total volume infused is greater than 0 mL, 1 infusion will be counted for that day.
- Total Number of Dose Interruptions will be determined for each subject by the number of times the IV was not completed in OLE, or segment outcome of the infusion was interrupted in parent study.
- Dose Strength (mg/kg) will be calculated for each subject at each OLE visit and each visit in parent study separately as follows:
 - For each OLE visit, dose (mg) recorded on the Study Drug Exposure CRF will be divided by the weight (kg) at that visit (Vital Signs CRF). If the dose (mg) is missing but the total duration of infusion is at least 50 minutes which is the lower limit of the protocol specified time (i.e. 60 min – 10 min), and IV completed is marked “Yes” then dose strength will be imputed to be equal to the planned dose strength (described below).
 - For each visit in parent study, the total dose (mg) reported will be divided by the weight used to calculate dose strength for that visit. If Current Visit is marked for Weight Used to determine dose and no corresponding weight is available from the vital sign page then the screening/baseline weight will be assigned as the weight used to calculate total dose. Dose strength will only be calculated where both the total dose and weight used are available.

Once visit/individual specific dose strengths are determined, subjects will be assigned a single average dose strength value across all visits to be used for summary statistics in the table.

- Percent of Planned Dose Strength will be determined by dividing the average dose strength per visit by the average planned dose strength per visit for each subject. Calculation of average dose strength is described above. Planned dose strength will be assigned by visit based on NEOD001 dose level. The average of planned dose strength will be the average of the individual planned dose strength calculated at each visit.

Once visit/individual specific percent of planned dose strength are determined, subjects will be assigned a single average percent of planned dose strength value across all visits to be used for summary statistics in the table.

- Total Number of Dose Reductions will be determined for each subject by the number of times the percent of planned dose was less than 100.

In addition, duration of exposure (months) will be calculated including treatment delays and interruptions as: $(\text{last dose date} - \text{first dose date} + 1) / 30.4375$. Duration will be calculated from the first infusion in the original parent study (NEOD001-001) and separately from the first infusion in the OLE. Each duration of exposure will be summarized using descriptive statistics. The number and percentage of subjects with duration of exposure in the following categories will be summarized:

- <3 months
- ≥ 3 and <6 months
- ≥ 6 and <9 months
- ≥ 9 and <12 months
- ≥ 12 and <15 months
- ≥ 15 months and <18 months
- ≥ 18 months and <21 months
- ≥ 21 months and <24 months
- ≥ 24 months

Additional 3-month intervals may be added based on the available data. The number of total infusions will be summarized with similar categories, replacing months with infusions.

All recorded and derived exposure data will be presented in a by-subject data listing.

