1.3.2 Clinical Safety

The safety and tolerability of NEOD001 have been investigated in the Phase 1/2 study (Study NEOD001-001) in the US, and are being investigated in the following ongoing global studies:

- Phase 1/2 open-label extension study (Study NEOD001-OLE001)
- Phase 2b study (Study NEOD001-201)
- Phase 3 study (Study NEOD001-CL002)

Study NEOD001-001 was a Phase 1/2 open-label, dose escalation study of the IV administration of single-agent NEOD001 in subjects with AL amyloidosis, which enrolled 27 subjects in the Escalation Phase in 7 cohorts (evaluating dose levels from 0.5 mg/kg to 24.0 mg/kg) and enrolled an additional 42 subjects in the Expansion Phase. The most frequently reported treatment-emergent adverse events (TEAEs) overall in Study NEOD001-001 (occurring in $\geq 10\%$ of subjects [N=69], regardless of relationship to NEOD001) were fatigue, nausea, upper respiratory tract infection, diarrhea, anemia, blood creatinine increased, dizziness, constipation, cough, headache, edema peripheral, vomiting, pain in extremity, back pain, dyspnea, edema, muscle spasms, rash, and urinary tract infection (Gertz et al, 2016). No confirmed anti-NEOD001 antibodies were detected. No dose-limiting toxicities (DLTs) or related serious adverse events (SAEs) were reported.

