5.3 DOSAGE, PREPARATION, AND ADMINISTRATION

Study drug consists of NEOD001. The NEOD001 dose is 24 mg/kg; however, the maximum dose administered is not to exceed 2500 mg. Therefore, subjects with a weight of 104.2 kg or greater will receive the maximum dose of 2500 mg. The subject's weight during Screening may be used for calculation of the first dose. Subsequent doses may be calculated based on the current weight at that visit or using the baseline weight, based on the site's institutional guidelines. A change of $\pm 10\%$ from the weight being used for dosing should trigger recalculation of the dose based on the new weight unless thought to be exclusively due to fluid fluctuation (e.g., edema).

Each vial of 500 mg of NEOD001 will be reconstituted with 9.6 mL sterile WFI to a concentration of 50 mg/mL resulting in a buffered, isotonic, preservative-free solution with a total extractable volume of 10 mL. Study drug will be prepared in a 250-mL IV bag of 0.9% saline. The equivalent volume of reconstituted NEOD001 will be withdrawn prior to transferring the drug solution into the IV bag, such that the total IV bag volume will be 250 mL.

Refer to the Pharmacy Manual for complete information on preparing and administering the study drug.

The study drug should only be administered in settings where emergency resuscitative equipment and personnel trained in the management of anaphylaxis are immediately available to treat systemic reactions under the direct supervision of a physician.

The study drug will be administered once every 28 (± 5) days at the infusion duration established in Study NEOD001-001 or over 60 (± 10) minutes. The length of the infusion may be extended over a longer period of time as clinically indicated.

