2.2.2. Study Drug

Study drug consists of NEOD001. The NEOD001 dose is 24 mg/kg (not to exceed 2500 mg) and will be administered once every 28 (±5) days using the infusion duration established in Study NEOD001-001 or over 60 (±10) minutes. The length of the infusion may be extended over a longer period of time when it is clinically indicated. Each vial of 500 mg of NEOD001 will be reconstituted with 9.6 mL sterile water for injection to a concentration of 50 mg/mL, resulting in a buffered, isotonic, preservative-free solution with a total extractable volume of 10 mL. Study drug will be prepared in a 250 mL intravenous (IV) bag of 0.9% saline. The equivalent volume of reconstituted NEOD001 will be withdrawn from the IV bag prior to transferring the drug solution into the IV bag, such that the total IV bag volume will be 250 mL.

Please refer to the protocol for complete product details.

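### SAP 9.1 takes planned dose strength from the mg/kg level without the 2500 mg maximum, so a full capped dose in the extension scores below 100% and counts as a dose reduction

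*SAP*

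**What the plan says.** Protocol 5.3 sets the dose and its limit together: "The NEOD001 dose is 24 mg/kg; however, the maximum dose administered is not to exceed 2500 mg". It also gives the weight at which the limit takes over: "subjects with a weight of 104.2 kg or greater will receive the maximum dose of 2500 mg". SAP 2.2.2 repeats the rule: "The NEOD001 dose is 24 mg/kg (not to exceed 2500 mg) and will be administered once every 28 (±5) days".

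SAP 9.1 builds the exposure summary in four steps.

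- **Dose strength received, extension visits:** "dose (mg) recorded on the Study Drug Exposure CRF will be divided by the weight (kg) at that visit (Vital Signs CRF".
- **Planned dose strength:** "Planned dose strength will be assigned by visit based on NEOD001 dose level". The 2500 mg limit is not mentioned.
- **Percent of planned dose strength:** "dividing the average dose strength per visit by the average planned dose strength per visit for each subject".
- **Dose reductions:** for each subject, the number of occasions on which the percentage is under 100.

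One exception is given. If the mg dose is missing, the infusion lasted at least 50 minutes and it was marked complete, dose strength is set equal to planned.

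Elsewhere the documents use dose level for a mg/kg figure. Protocol 1.3.2 describes the parent study as "evaluating dose levels from 0.5 mg/kg to 24.0 mg/kg", and SAP Table 6 labels the extension group 24 mg/kg.

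**The concern.** The maximum lowers the numerator for a heavy subject but not the denominator. Once 24 mg/kg would exceed 2500 mg, the planned figure is a dose that the protocol does not allow, and a complete, correct infusion is reported as a shortfall.

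The reduction count matters more than the percentage. The primary objective is long-term safety and tolerability, and a dose reduction is read as tolerability information: protocol 5.4.2 and 5.4.3 provide for 50% reductions after certain adverse events. Under SAP 9.1 a correctly capped visit enters the same count as one of those reductions. The adverse event tables in SAP 9.2.2 and 9.2.6 take reductions from the investigator's action-taken field, so a subject could have 36 reductions in the exposure table and none in the adverse event table. The decision in SAP 8 and 11 to drop efficacy summaries does not remove the exposure tables.

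**Working it through.** **Inputs.** Level 24 mg/kg and maximum 2500 mg (protocol 5.3, SAP 2.2.2); 36 scheduled infusions (protocol 6.1.2); numerator, denominator and counting rule (SAP 9.1). The weights below are illustrative.

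**The protocol's own figure.** 2500 / 24 = 104.17 kg, which rounds to the stated 104.2 kg.

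**Percent of planned as SAP 9.1 reads**, for weight W and a dose calculated on the visit weight:

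100 × [min(24 × W, 2500) / W] / 24

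| W (kg) | Dose given (mg) | Strength received (mg/kg) | Percent of 24 mg/kg | Visits counted as reductions |
|---|---|---|---|---|
| 100 | 2400 | 24.00 | 100.0 | 0 of 36 |
| 104.2 | 2500 | 23.99 | 99.97 | 36 of 36 |
| 110 | 2500 | 22.73 | 94.7 | 36 of 36 |
| 120 | 2500 | 20.83 | 86.8 | 36 of 36 |
| 130 | 2500 | 19.23 | 80.1 | 36 of 36 |
| 150 | 2500 | 16.67 | 69.4 | 36 of 36 |

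The last column assumes all 36 infusions were given with a recorded dose at that weight. For a recorded dose at a visit weight above 104.17 kg the result must be below 100%, because the dose cannot exceed 2500 mg and 2500 / W is then below 24.

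**Imputed visits.** A visit set to planned strength scores 100% and is not counted. At 120 kg with 35 of 36 visits imputed, the subject's average is (86.81 + 35 × 100) / 36 = 99.6%.

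**Dosing weight different from visit weight.** Protocol 5.3 allows dosing on baseline weight until a 10% change. A subject dosed on 106 kg who weighs 98 kg at the visit shows (2500 / 98) / 24 = 106.3%. The weight that decides the result is therefore the visit weight.

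**With a capped denominator.** Taking planned strength as min(24, 2500 / W) with the same W in both terms, every row of the table becomes 100.0% with 0 of 36 visits counted. If the two weights differ, a new error appears: for a subject dosed on 120 kg and weighing 110 kg (an 8.3% change), dosing weight in the denominator and visit weight in the numerator give (2500 / 110) / (2500 / 120) = 120 / 110 = 109%.

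**The case against.** The strongest reply is that SAP 9.1 is silent rather than wrong. It never writes 24 mg/kg as the planned value, it speaks of planned strength being worked out at each visit, and SAP 2.2.2 states the maximum, so a programmer could carry the limit across. That is possible, and it stands as a reason not to say that the SAP excludes the maximum outright. But nothing in SAP 9.1 tells the programmer to apply it, and both documents use dose level for a mg/kg figure.

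A second reply is that a capped subject does receive fewer mg/kg than 24, so comparison with the nominal level is a legitimate description. That holds for the dose-strength summary itself, where 20.83 mg/kg at 120 kg is correct. It does not hold for a percentage of what was planned, or for a count of reductions.

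A third reply is that real reductions remain visible elsewhere: in the action-taken summaries, in the adverse event listing of dose changes, and in the administration listing that protocol 8.2 requires to flag modifications. This is correct. A reader might infer that toxicity-driven reductions would be lost from the safety report; the documents do not support that. Those outputs do not, however, correct the exposure table.

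Finally, the summaries are descriptive, medians and quartiles are shown beside means (SAP 4.1), and SAP 9 plans no inferential safety comparison unless otherwise specified. This limits the weight of the point.

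**Conclusion.** The point holds for extension visits with a recorded dose and a visit weight above 104.17 kg, on the plain reading of SAP 9.1. Such a visit falls below 100% of planned after a full protocol dose, by 5.3 points at 110 kg, 13.2 at 120 kg and 19.9 at 130 kg, and is counted as a dose reduction. The maximum is 36 false reductions per subject.

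Three stronger readings are not supported.

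- **That every subject above 104.2 kg always scores below 100%.** Imputed visits score 100%, and a subject dosed on a heavier baseline weight can score above 100% once the visit weight falls under the threshold.
- **That the group result is materially distorted.** The documents give no weight distribution, and the number affected could be zero. If 5% to 15% of subjects weighed 120 kg (an assumption), the mean would fall by 0.05 × 13.2 = 0.7 to 0.15 × 13.2 = 2.0 points. The subject-level percentages and the reduction count are the main problem: with about 70 subjects, a few heavy ones could dominate the count.
- **That the combined parent-plus-extension summary is wrong by the same amount.** The documents state no maximum for the parent study, so the effect on its visits is unknown.

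The change is worth making: it is small, and it concerns a table that bears on the primary objective. No endpoint decision depends on it.

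**What to change.** In SAP 9.1, for extension visits, define planned dose strength as the smaller of 24 mg/kg and 2500 mg divided by weight. Use the same weight in numerator and denominator: the visit weight, as the SAP now has it, or the dosing weight in both terms if the extension case report form records it. The documents describe a weight-used field only for the parent study, so this needs checking before the second option is chosen.

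Use the capped value both for percent of planned dose strength and for the dose-reduction count. The imputation rule refers to the same planned value and will follow it. Apply a maximum to parent-study visits only if that study's protocol had one.

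The cost is a sentence or two in the SAP and a one-line change to the derivation. With visit weight, no new data are needed. Some discrepancy will then remain where the dose was calculated on baseline weight: an uncapped subject dosed on 80 kg and weighing 86 kg shows 80 / 86 = 93.0% and is counted as reduced. Only dosing weight in both terms removes that.

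The change concerns the analysis derivation alone and takes no view on the dose or its maximum.

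### SAP 9.1 counts a full extension-study dose as a dose reduction whenever the subject weighs more at the visit than the weight the dose was calculated on

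*SAP*

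**What the plan says.** SAP 9.1 (Extent of Exposure) builds the count in three steps.

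- **Dose strength, OLE visits:** "dose (mg) recorded on the Study Drug Exposure CRF will be divided by the weight (kg) at that visit (Vital Signs CRF"). For parent-study visits the basis differs: "the total dose (mg) reported will be divided by the weight used to calculate dose strength for that visit".
- **Planned dose strength:** "Planned dose strength will be assigned by visit based on NEOD001 dose level". The section adds that "The average of planned dose strength will be the average of the individual planned dose strength calculated at each visit".
- **Reductions:** "Dose Reductions will be determined for each subject by the number of times the percent of planned dose was less than 100". No tolerance appears here or elsewhere in the SAP.

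SAP 2.2.2 gives the OLE dose: "The NEOD001 dose is 24 mg/kg (not to exceed 2500 mg").

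Protocol 5.3 permits the Screening weight for the first dose. For later doses it permits either the weight on the day or the baseline weight, according to local practice. A 10% departure from the dosing weight should prompt recalculation, except where the change is attributed wholly to fluid. Protocol 5.4.2 and 5.4.3 describe dose reductions, and in both the reduction is 50%.

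**The concern.** The numerator of the OLE percentage uses a weight that the protocol does not require sites to dose on. Where the dosing weight is an earlier and lower one, a subject who received everything the protocol called for is recorded as having had a reduction. Weight loss pushes the percentage above 100 and adds nothing to the count, so the errors do not cancel.

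Weight drift is foreseeable in this study. Subjects may receive up to 36 infusions. Protocol 1.3.2 lists edema and peripheral edema among the events seen in at least 10% of parent-study subjects, and fluid change is the stated ground for not recalculating.

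The primary objective is long-term safety and tolerability, and a reader will take the number of dose reductions as a tolerability measure. The exposure table could also disagree, without explanation, with the SAP 9.2.6 table of adverse events leading to dose reduction, which uses the recorded action taken. In addition, the combined parent-plus-OLE count would rest on two different weight bases. The SAP states that difference openly but does not reconcile it.

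**Working it through.** **Inputs.** Dose level 24 mg/kg and maximum 2500 mg (Protocol 5.3, SAP 2.2.2); recalculation trigger 10% (Protocol 5.3); reduction size 50% (Protocol 5.4.2, 5.4.3); counting rule under 100% (SAP 9.1).

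**The plan's own figure.** Protocol 5.3 says the maximum applies from 104.2 kg. 2500 / 24 = 104.17 kg, which agrees.

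**Full dose on an earlier weight, below the cap.** With dosing weight W and visit weight W(1 + g):

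percent of planned = [24W / (W(1 + g))] / 24 = 1 / (1 + g)

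The result does not depend on W.

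| Weight change since dosing weight | Percent of planned | Counted as a reduction? |
|---|---|---|
| +1% | 1/1.01 = 99.0% | yes |
| +5% | 1/1.05 = 95.2% | yes |
| +10% | 1/1.10 = 90.9% | yes |
| −5% | 1/0.95 = 105.3% | no |

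Example: a dosing weight of 80 kg gives 24 × 80 = 1920 mg. At a visit weight of 84 kg, 1920 / 84 = 22.86 mg/kg, and 22.86 / 24 = 95.2%.

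**A true 50% reduction on the same basis.** At +10% weight, 0.5 / 1.10 = 45.5%. At −10%, 0.5 / 0.90 = 55.6%. Over ±10% weight change, full doses score 90.9% to 111.1% (1/1.10 to 1/0.90). The two groups do not overlap, but a cut at 100% counts the halved doses together with every full dose given after a gain.

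**Capped doses.** At 110 kg, 2500 / 110 = 22.73 mg/kg. Against a flat 24 mg/kg this is 94.7% and is counted. Against a cap-adjusted planned strength of 2500 / 110 it is 100% and is not. SAP 9.1 does not say which applies.

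**Can a different cut separate the groups using visit weight alone?** Take the planned dose as min(24 × visit weight, 2500 mg) and cut at 75%. Over dosing weights of 40 to 150 kg, with weight changes just inside ±10%, full doses score 90.9% to 111.1% and half doses 45.5% to 55.5%, so the cut separates them throughout. Its limits are:

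- a full dose falls below 75% only if the gain exceeds 1/0.75 − 1 = 33.3%;
- a half dose rises above 75% only if the loss exceeds 1 − 0.5/0.75 = 33.3%.

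**Rounding (assumption; Protocol 5.3 gives no rule).** Rounding to the nearest 10 mg loses at most 5 mg, which at 50 kg is 5 / 1200 = 0.42%. Rounding to the nearest 50 mg loses at most 25 mg, or 25 / 1200 = 2.08% at 50 kg and 25 / 2400 = 1.04% at 100 kg.

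**The case against.** The strongest counter-argument is that the counting rule refers to percent of planned dose, while the defined variable is percent of planned dose strength, described as a ratio of per-subject averages. If the former meant mg given over mg planned, full doses would score 100%. The same would follow if the planned strength at each visit were worked back from the planned mg. This does not rescue the rule. SAP 9.1 defines no mg-over-mg variable. Counting occasions makes sense only visit by visit, and the section itself says "Once visit/individual specific percent of planned dose strength are determined, subjects will be assigned a single average percent of planned dose strength value". Assigning planned strength by dose level points to a flat 24 mg/kg. What stands is that the wording needs tightening whichever meaning was intended.

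The second argument is that the effect is of unknown size and may be nil, since sites may dose on current weight. That is correct. A 10% gain without recalculation would normally arise only under the fluid exception, so most miscounted doses should score above 90.9%.

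The third is that true reductions are visible elsewhere: the recorded exposure data, the dose modifications flagged under Protocol 8.2, and the adverse event tables. This stands and limits the damage. However, the by-subject listing also shows derived exposure data, and those derived values would inherit the miscount.

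Finally, the OLE basis may simply reflect what was collected, since SAP 9.1 mentions a weight-used field only for the parent study. That is a fair point, and the remedy has to work without that field.

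**Conclusion.** The concern holds. As written, SAP 9.1 counts an uncapped full OLE dose as a reduction after any gain over the dosing weight, at 99.0% of planned after a 1% gain and 95.2% after 5%. It cannot distinguish these from the protocol's 50% reductions. The conclusion rests on reading the percentage per visit against the 24 mg/kg dose level, which is the only reading the section's definitions support. Treatment of capped doses is an ambiguity, not a demonstrated error.

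The number of infusions or subjects affected cannot be derived, because the documents give no weight data and no share of sites dosing on baseline weight. With current-weight, uncapped and unrounded dosing it is zero. The fault is confined to one descriptive count (and its derived listing values) that is not itself a primary endpoint. It should be corrected because it sits in the exposure summary of a tolerability study and is cheap to put right.

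**What to change.** Amend SAP 9.1 as follows. None of this changes a dosing rule.

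1. Define percent of planned dose per visit, in both studies, as recorded mg divided by the smaller of (protocol dose level × weight used for dosing) and that study's protocol maximum dose. The maximum has no effect where a study sets none; the documents state one only for the OLE.
2. Count a reduction only when the result is below 100% minus a stated tolerance matched to the pharmacy rounding rule. A tolerance of 1% covers rounding to the nearest 10 mg; rounding to the nearest 50 mg would need about 2.1% at 50 kg.
3. If the OLE dosing weight was not collected, use the cap-adjusted dose at the visit weight with a cut of under 75% for OLE visits. State the 33.3% weight-change limits, and state that shortfalls scoring 75% or more are not counted.
4. If recorded mg is the amount actually infused, the 75% cut may also catch incomplete infusions. SAP 9.1 already counts these as interruptions ("by the number of times the IV was not completed in OLE"), so show them separately.
5. Use the adverse-event action field for dose reduced only as a cross-check. One event can span several reduced infusions, because Protocol 5.4.3 leaves the duration of a reduction to the investigator.

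The cost is SAP wording plus a changed denominator and cut-off in the derivation code. The fallback in step 3 needs no new data; step 1 needs the OLE dosing weight, which may not exist.
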